7. ANALYSIS INTERPRETATION

All the analyses performed during this study will be descriptive.

8. CONDUCT OF ANALYSES

8.1. Sequence of analyses

The analyses will be performed stepwise:

- An interim analysis to allow an internal decision for the choice of the booster dose in study Malaria-102 will be performed as soon as the results of the challenge phase will be available on data as clean as possible. This analysis will be descriptive and performed on the Adapted PPS for analysis of efficacy.
- When all the remaining data up to Day 376 will be available, the main analysis will be performed. An integrated study report will be written.

8.2. Statistical considerations for interim analyses

A descriptive analysis to evaluate VE against infection of *P. falciparum* will be performed on the Adapted PPS for analysis of efficacy at the time of the interim analysis. Note that the main objective of the study linked to this endpoint will be analysed at the end of the study, on the PPS for analysis of immunogenicity and efficacy and can output different results.

9. CHANGES FROM PLANNED ANALYSES

The Total vaccinated cohort (TVC) defined in the protocol has been replaced by the Intent-To-Treat Set (ITTS) to include both subjects vaccinated and subjects from the infectivity control group in the same cohort.

An interim analysis has been added to allow an internal decision for the choice of the booster dose in study Malaria-102. This analysis will be descriptive and performed on data as cleaned as possible.

To allow an interim analysis as close as possible to the main analysis, an Adapted PPS for analysis of efficacy has been created.

An analysis of concomitant vaccination has been added to assess any effect on immune response or safety.

A Solicited Safety Set has been added in the analysis set section to fit with the new statistical rules and layouts applicable from the 12th of November.

10. LIST OF FINAL REPORT TABLES, LISTINGS AND FIGURES

The TFL TOC provides the list of tables/listings and figures needed for the study report. It also identifies the tables eligible for each analyses and their role (synopsis, in-text, post-text, SHS, CTRS, Annex). Note that all TFL aimed to be included as post-text are noted as post-text even if these are tabulations of individual data such as listings of SAEs. The post-text material contains all source material for the study report and accordingly a post-text table may be redundant with an in-text table.

11. ANNEX 1 STANDARD DATA DERIVATION RULE AND STATISTICAL METHODS

11.1. Statistical Method References

The exact two-sided 95% CIs for a proportion within a group will be the Clopper-Pearson exact CI [Clopper CJ, Pearson ES. The use of confidence or fiducial limits illustrated in the case of binomial. *Biometrika*. 1934;26:404-413].

11.2. Standard data derivation

11.2.1. Date derivation

- SAS date derived from a character date: In case day is missing, 15 is used. In case day & month are missing, 30 June is used.
- Onset day for an event (AE, medication, vaccination): The onset day is the number of days between the last study vaccination & the onset/start date of the event. This is 1 for an event starting on the same day as a vaccination. See SAS date derived in case the start date of the event is incomplete.
- Duration: Duration of an event is expressed in days. It is the number of days between the start & the stop dates + 1. Therefore duration is 1 day for an event starting & ending on the same day.

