9.3. Detecting and recording adverse events, serious adverse events and pregnancies

9.3.1. Time period for detecting and recording adverse events, serious adverse events and pregnancies

All AEs starting within 30 days following administration of each dose of study vaccines (Day 0 to Day 29) must be recorded into the appropriate section of the eCRF, irrespective of intensity or whether or not they are considered vaccination-related.

For vaccinated subjects, the time period for collecting and recording SAEs will begin at the first receipt of study vaccine (Day 0) and will end at the last study visit (Day 376). For the infectivity controls group, the time period for collecting and recording SAEs will begin on the first day of the sporozoite challenge (Day 286) and will end at the last study visit (Day 314). See Section 9.4 for instructions on reporting of SAEs.

All AEs/SAEs leading to withdrawal from the study will be collected and recorded from the time of the first receipt of study vaccines (Day 0) for AduFx, 2PedFx, PedFx, Adu2Fx, and Adu1Fx groups.

In addition to the above-mentioned reporting requirements and in order to fulfill international reporting obligations, SAEs that are related to study participation (i.e. protocol-mandated procedures, invasive tests, a change from existing therapy) or are related to a concurrent GSK medication/vaccine will be collected and recorded from the time the subject consents to participate (i.e. Screening) in the study until she/he is discharged from the study.

For vaccinated subjects, the time period for collecting and recording pregnancies will begin at the first receipt of study vaccines (Day 0) and will end at the last study visit (Day 376). For the infectivity controls group, the time period for collecting and recording pregnancies will begin on the first day of the sporozoite challenge (Day 286) and will end at the last study visit (Day 314). See section 9.4 for instructions on reporting of pregnancies.

For vaccinated subjects, the time period for collecting and recording of AEs of specific interest (meningitis and pIMDs) will begin at the first receipt of study vaccines (Day 0) and will end at the last study visit (Day 376). See section 9.4 for instructions on reporting of pIMDs.

An overview of the protocol-required reporting periods for AEs, SAEs and pregnancies is given in [Table 25](#), [Table 26](#) and [Table 27](#).

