4.2.3. Safety

- Safety and reactogenicity of the investigational vaccine for each vaccination schedule:
 - Occurrence of solicited local and general AEs within seven days (day of vaccination and six subsequent days) after each vaccination.
 - Occurrence of unsolicited AEs within 30 days (day of vaccination and 29 subsequent days) after each vaccination, according to the Medical Dictionary for Regulatory Activities (MedDRA) classification.
 - Occurrence of AEs within 30 days (day of challenge and 29 subsequent days) after challenge, according to the MedDRA classification.
 - Occurrence of SAEs (all, fatal, related to investigational vaccine) within 30 days (day of vaccination and 29 subsequent days) after each vaccination, according to the MedDRA classification.
 - Occurrence of SAEs (all, fatal, related to investigational vaccine) during the whole study period (from Dose 1 [Day 0] up to study conclusion [Day 376]), according to the MedDRA classification.
 - Occurrence of AEs and SAEs leading to withdrawal from further vaccination from Dose 1 (Day 0) up to study conclusion (Day 376), according to the MedDRA classification, for each vaccinated subject.
 - Occurrence of pIMDs from Dose 1 (Day 0) up to study conclusion (Day 376), according to the MedDRA classification, for each vaccinated subject.
 - Occurrence of meningitis from Dose 1 (Day 0) up to study conclusion (Day 376), according to the MedDRA classification, for each vaccinated subject.
 - Occurrence of abnormal laboratory values at screening, Day 35, Day 58, Day 203, Day 226, the day of first parasitemia, and Day 314 for each vaccinated subject and at screening, the day of first parasitemia and Day 314 for the infectivity control subjects.

- Safety after sporozoite challenge in the infectivity control group.
 - Occurrence of AEs within 30 days (day of challenge and 29 subsequent days) after challenge, according to the MedDRA classification.
 - Occurrence of SAEs (all, fatal, related) from day of challenge (Day 286) to the end of the challenge phase (Day 314), according to the MedDRA classification.

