5.2.2. Elimination from the Solicited Safety Set

Code 1030 (study vaccine not administered at all), code 900 (invalid informed consent or fraud data) and code 1160 (no post-vaccination solicited safety data) will be used for identifying subjects eliminated from the solicited safety set.

5.2.3. Elimination from the PPS for analysis of immunogenicity and efficacy**5.2.3.1. Excluded subjects**

A subject will be excluded from the PPS analysis of immunogenicity and efficacy analysis under the following conditions

Code	Condition under which the code is used
900	Invalid informed consent or fraud data
1030	Study vaccine not administered at all
1040	Administration of concomitant vaccine(s) forbidden in the protocol 
 • Any investigational or non-registered vaccine other than the study vaccines used during the study period. • A vaccine not foreseen by the study protocol administered during the period starting seven days before each dose and ending seven days after each dose of vaccines administration.
1070	Vaccination not according to protocol 
 • Incomplete vaccination course before treatment withdrawal or subject study conclusion. • Administration not according to protocol for reason specified by the investigator, other than side, site and route. • Wrong replacement or study vaccine administered (not compatible with the vaccine regimen associated to the treatment number). • Study vaccine RTS,S/AS01 not prepared as per protocol

Code	Condition under which the code is used
1080	Good Manufacturing Practice No-Go: Vaccine temperature deviation
1090	Expired vaccine administered
2010	Protocol violation (inclusion/exclusion criteria) 
 Eligibility criteria not met with an impact on immunogenicity data

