11.2.2. Dose number

- The study dose number is defined in reference to the number of study visits at which vaccination occurred. More specifically dose 1 refers to all vaccines administered at the first vaccination visit while dose 2 corresponds to all vaccinations administered at the second vaccination visit even if this is the first time a product is administered to the subject.
- Relative dose: the relative dose for an event (AE, medication, vaccination) is the most recent study dose given before an event. In case the event takes place on the day a study dose is given, the related dose will be that of the study dose, even if the event actually took place before vaccination. For instance, if an AE begins on the day of the study vaccination but prior to administration of the vaccine, it will be assigned to this dose. In case a study dose is not administered (eg dose 2) and an event occurs after the subsequent study dose (eg 3rd study dose), the relative dose of the event will be study dose associated to the subsequent study dose (eg dose 3).
- The number of doses for a product is the number of times the product was administered to a subject.
- The incidence per dose is the number of vaccination visits at which an event was reported among all vaccination visits.

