Note that for all tables described in this section, the way the percentage of subjects will be derived will depend on the event analysed (see table below for details). As a result, the N value will differ from one table to another.

Event	N used for deriving % per subject for Vaccination phase	N used for deriving % per dose for Vaccination phase
Concomitant vaccination	All subjects with study vaccine administered	All study visits with study vaccine administered
Solicited general symptom	All subjects with at least one solicited general symptom documented as either present or absent (i.e., symptom screen completed)	All study visits with study vaccine administered and with at least one solicited general symptom documented as either present or absent (i.e., symptom screen completed)
Solicited local symptom	All subjects with at least one solicited local symptom documented as either present or absent (i.e., symptom screen completed)	All study visits with study vaccine administered and with at least one solicited local symptom documented as either present or absent (i.e., symptom screen completed)
Unsolicited symptom	All subjects with study vaccine administered	All study visits with study vaccine administered
Concomitant medication	All subjects with study vaccine administered	All study visits with study vaccine administered

- Related dose: The related dose for an event (e.g., AE, medication, vaccination,...) is the study dose given before an event. In case the event takes place on a day a study dose is given, if the investigator has indicated the timing (before or after the vaccination) the related dose for this event is the most recent study dose given before this event. If the investigator has not indicated the timing, the related dose will be that of the study dose even if the event actually took place before.

Number of decimals displayed:

The following decimal description from the decision rules will be used for demography, efficacy, immunogenicity and safety/reactogenicity results.

Display Table	Parameters	Number of decimal digits
Demographic characteristics	Mean, median age	1
Demographic characteristics	SD (age)	1
Reactogenicity	Mean, Min, Q1, Median, Q3, Max for duration	1
All summaries	p-value	3

Percentages and their corresponding confidence limits will be displayed with:

- no decimals when there are fewer than 50 subjects in each tabulated group
- one decimal when there are at least 50 subjects in at least one tabulated group

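### Incomplete start dates of adverse events: the mid-month rule in SAP 11.2.1 has no bound at the dose, challenge or stop date, so an event can be dated before the dose or challenge it followed

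*SAP*

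**What the plan says.** SAP 11.2.1 gives one rule for every incomplete date: "In case day is missing, 15 is used. In case day & month are missing, 30 June is used". The rule then enters the onset day. "The onset day is the number of days between the last study vaccination & the onset/start date of the event", and for incomplete start dates the reader is told: "See SAS date derived in case the start date of the event is incomplete". SAP 11.2.2 builds dose assignment on this: "the relative dose for an event (AE, medication, vaccination) is the most recent study dose given before an event".

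The safety tables are defined by windows. SAP 4.2.3 lists "Occurrence of unsolicited AEs within 30 days (day of vaccination and 29 subsequent days) after each vaccination" and a window of the same length after challenge. SAP 6.5.1 adds SAEs from Day 286 to Day 314. Onset day is counted from vaccination only; none is defined from the challenge.

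The only nearby safeguard concerns events dated on a dosing day. SAP 11.2.5 begins it with "In case the event takes place on a day a study dose is given, if the investigator has indicated the timing", and SAP 11.2.2 has a similar rule. Neither reaches an event imputed to an earlier day. SAP Amendment 1 updated the standard computation rules but kept this date rule.

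**The concern.** The 15th is a neutral guess for a date about which nothing else is known. Here something else usually is known. Protocol 9.3.1 has unsolicited AEs recorded because they start within Day 0-29 of a dose. SAE collection opens at Dose 1 for vaccinees and at challenge for controls, apart from SAEs related to study participation or to a concurrent sponsor product. A start date before Dose 1 is thus impossible for nearly every recorded vaccinee event, yet the rule can produce one.

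At stake are the secondary safety tables: unsolicited AEs and SAEs within 30 days of vaccination, AEs within 30 days of challenge, and SAEs in the challenge phase.

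**Working it through.** The plan gives no figure to reproduce. The check applies the written rule to every possible date.

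**Inputs from the documents**
- Day missing becomes the 15th; day and month missing become 30 June (SAP 11.2.1).
- The window is Day 0-29 (SAP 4.2.3).
- Dose 2 is 28 ± 7 days after Dose 1 in four groups. The Month 7 dose is 168 ± 14 days after Dose 2 (196 ± 14 days after Dose 1 in Adu1Fx). Challenge is 90 + 14 days after the last dose (SAP Tables 1 and 2).

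**Assumptions, not in the documents**
- The dose or challenge (the reference) is equally likely on each of 365 days.
- True onset is uniform over Day 0-29.
- The month is known and the day missing.

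**Example.** Dose on 20 September, AE on 25 September, recorded as September only. The imputed date is 15 September, 5 days before the dose.

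**Dated before the reference.** There are 365 × 30 = 10,950 combinations. If the reference is day d ≥ 16 of a month of M days, each of the M − d + 1 onset days left in that month is moved to the 15th. Summed over d, this is (M − 15)(M − 14)/2: 136 for M = 31, 120 for M = 30 and 91 for M = 28. Over the year, 7 × 136 + 4 × 120 + 91 = 1,523, and 1,523 / 10,950 = **13.9%**.

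**Dated beyond Day 29.** An onset in the next month goes to that month's 15th, which is M − d + 15 days after the reference. This exceeds 29 when d ≤ M − 15. The affected onset days then number 1, 2, ..., 14, or 105 per month (the February end effects cancel). So 12 × 105 = 1,260, and 1,260 / 10,950 = **11.5%**.

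**Kept.** 10,950 − 1,523 − 1,260 = 8,167, or 74.6%. With a floor at the reference date in the same month, the 1,523 return: 9,690 / 10,950 = 88.5%. The 11.5% stays out.

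**Where the early-dated events go.** The shift is 1 day (reference on the 16th) to 16 days (on the 31st) before the reference.
- *Dose 1:* no earlier dose exists, so the event leaves the table.
- *Dose 2 at Day 28:* the event lands 12 to 27 days after Dose 1, always inside that window. It is credited to the wrong dose but kept in a table of events within 30 days of any vaccination. At a 21-day gap the same holds (Day 5 to 20). At 35 days it lands on Day 19 to 34 and stays in only if the reference is on the 21st or later: 7 × 66 + 4 × 55 + 36 = 718, and 718 / 1,523 = 47%.
- *Month 7 dose:* the event is at least 168 − 14 − 16 = 138 days after the previous dose, so it leaves the table.
- *Challenge:* the event is 74 to 89 days after the last dose (90 minus 16 to 1), so it leaves both the post-dose and post-challenge tables. Controls have no dose to attach to.

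**Year only known.** With 30 June imputed, 46.4% fall before the reference, 45.3% after the window and 8.2% (30/365) inside it.

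**The case against.** **Incomplete dates should be rare.** Unsolicited AEs for Day 0-29 are on diary cards verified with the subject (protocol 6.6.18). Challenged subjects are seen daily from Day 291 to Day 304 and then mostly every two days. SAEs are reported within 24 hours, and source data are verified. This stands: the percentages are per incomplete date, and the total effect may be very small. Year-only AE dates are remote.

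**A reader might infer that early vaccine reactions are systematically undercounted.** With onset confined to Day 0-6, the same count gives 7 × 91 + 4 × 84 + 70 = 1,043 of 365 × 7 = 2,555, or 40.8%, dated before the dose. The documents do not support that reading. The typical early reactions are solicited AEs, which SAP 11.2.5 analyses per dose from symptom sheets and the highest daily recording. The 40.8% could apply only to unsolicited events with the day missing.

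**A reader might infer a one-sided loss of SAEs.** SAEs are collected continuously from Dose 1, so events outside a window can also be moved into it. At a constant event rate (an assumption), 25.4% flow out and 25.4% flow in: 11.5% from before the window and 13.9% from after it. Only Dose 1 lacks the 11.5% from before. The whole-study SAE table loses only events dated before Dose 1, and the SAE listing still shows them.

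**A reader might infer that the rule moves subjects in or out of the primary efficacy set.** Code 1040 excludes on a condition, "A vaccine not foreseen by the study protocol administered during the period starting seven days before each dose and ending seven days after each dose", and code 2040 covers antimalarials before parasitemia. No text says that imputed dates drive either code, and the primary endpoint comes from smears at dated visits.

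The gap in the rule itself survives these points. Nothing in either document bounds the imputed date.

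**Conclusion.** A real but minor defect, confined to unsolicited AEs and SAEs with an incomplete start date. Followed as written, the rule can date such an event before the dose or challenge it followed. The event leaves the 30-day table after Dose 1, the Month 7 dose or the challenge, and is usually only misattributed after Dose 2 at Day 28.

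The size, 13.9% early and 11.5% late per month-only event, rests on evenly spread reference dates and onsets. The number of such events is unknown. Recorded non-serious AEs belong to a window by design, so misdating can only remove or reassign them; for SAEs no net undercount is shown beyond Dose 1. The finding does not bear on the primary efficacy result.

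**What to change.** Add to SAP 11.2.1, for adverse events only:

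> If the known part of an AE start date is the same month and year (or year) as a study vaccination or the challenge, and the record (before/after flag or stop date) does not show that it began earlier, impute the later of the default date and that vaccination or challenge date. The imputed start may not fall after the known stop date, nor before Dose 1 (challenge for controls) for events collected only from that point.

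Doses 1 and 2 can share a calendar month, and one year can hold several reference dates. Settle those cases from the record.

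Leave the rule for medications and vaccinations unchanged, and decide codes 1040 and 2040 by case review when a date is incomplete. A floor there would do harm. With challenge on 20 March, an antimalarial truly started on 31 March but known only as March would be dated to the challenge day, and the censoring formula in SAP 6.3.2.2 would give Day 1. An unplanned vaccine known only as March, with a dose on 25 March, would move from the 15th, outside the seven-day window, onto the dose day.

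The cost is one SAP addition and a small programming change. Doubtful events are counted as post-dose or post-challenge, and the 11.5% imputed past Day 29 is not recovered.

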11.2.2. Dose number

- The study dose number is defined in reference to the number of study visits at which vaccination occurred. More specifically dose 1 refers to all vaccines administered at the first vaccination visit while dose 2 corresponds to all vaccinations administered at the second vaccination visit even if this is the first time a product is administered to the subject.
- Relative dose: the relative dose for an event (AE, medication, vaccination) is the most recent study dose given before an event. In case the event takes place on the day a study dose is given, the related dose will be that of the study dose, even if the event actually took place before vaccination. For instance, if an AE begins on the day of the study vaccination but prior to administration of the vaccine, it will be assigned to this dose. In case a study dose is not administered (eg dose 2) and an event occurs after the subsequent study dose (eg 3rd study dose), the relative dose of the event will be study dose associated to the subsequent study dose (eg dose 3).
- The number of doses for a product is the number of times the product was administered to a subject.
- The incidence per dose is the number of vaccination visits at which an event was reported among all vaccination visits.

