Pain when taking blood samples	When taking the blood samples, the subject may feel faint; or experience mild pain, bruising, irritation or redness.	Subjects will be advised to inform or call the study doctor immediately if they have any side effects that they perceive as serious.
Risks associated with malaria challenge	The risks associated with the sporozoite challenge include local inflammatory reactions or potential allergic reactions to mosquito bites as well as the development of malaria infection. Transient abnormalities, such as fever, headache, mild anemia, leukopenia, splenomegaly, hepatic tenderness and fatigue, are expected consequences of malaria. The complications of malaria which can lead to kidney, liver or brain damage, and death, are seen during naturally acquired malaria when diagnosis and treatment are delayed and high levels of parasitemia develop.	Anti-malaria treatment will be administered to malaria infected subjects. Under the carefully controlled conditions of this study, the chance of serious illness or death from malaria infection is very small.

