9.1. Safety definitions

9.1.1. Definition of an adverse event

An AE is any untoward medical occurrence in a clinical investigation subject, temporally associated with the use of a medicinal product, whether or not considered related to the medicinal product.

An AE can therefore be any unfavorable and unintended sign (including an abnormal laboratory finding), symptom, or disease (new or exacerbated) temporally associated with the use of a medicinal product. For marketed medicinal products, this also includes failure to produce expected benefits (i.e. lack of efficacy), abuse or misuse.

Examples of an AE include:

- Significant or unexpected worsening or exacerbation of the condition/indication under study.
- Exacerbation of a chronic or intermittent pre-existing condition including either an increase in frequency and/or intensity of the condition.
- New conditions detected or diagnosed after investigational vaccines administration even though they may have been present prior to the start of the study.
- Signs, symptoms, or the clinical sequelae of a suspected interaction.
- Signs, symptoms, or the clinical sequelae of a suspected overdose of either investigational vaccines or a concurrent medication (overdose per se should not be reported as an AE/SAE).
- Signs, symptoms temporally associated with vaccines administration.
- Pre- or post-treatment events that occur as a result of protocol-mandated procedures (i.e. invasive procedures, modification of subject's previous therapeutic regimen).

AEs to be recorded as endpoints (solicited AEs) are described in Section 9.1.3. All other AEs will be recorded as UNSOLICITED AEs.

Examples of an AE DO NOT include:

- Medical or surgical procedures (e.g. endoscopy, appendectomy); the condition that leads to the procedure is an AE/SAE.
- Situations where an untoward medical occurrence did not occur (e.g. social and/or convenience admission to a hospital, admission for routine examination).
- Anticipated day-to-day fluctuations of pre-existing disease(s) or condition(s) present or detected at the start of the study that do not worsen.
- Pre-existing conditions or signs and/or symptoms present in a subject prior to the first study vaccination. These events will be recorded in the medical history section of the eCRF.

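### SAP 11.2.2 and 11.2.5 assign different doses to an AE recorded as starting before the injection on a vaccination day

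*SAP*

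**What the plan says.** SAP 11.2.2 (entry *Relative dose*) deals with events on a day when a dose is given: "the related dose will be that of the study dose, even if the event actually took place before vaccination". Its worked example removes any doubt: "if an AE begins on the day of the study vaccination but prior to administration of the vaccine, it will be assigned to this dose".

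SAP 11.2.5 (entry *Related dose*) covers the same situation differently. Where the investigator recorded whether the event came before or after the injection, "the related dose for this event is the most recent study dose given before this event". Only without that record does the rule fall back on the day itself: "If the investigator has not indicated the timing, the related dose will be that of the study dose".

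SAP 11.2.1 sets the onset day to 1 for any event that starts on the date of a vaccination, without asking whether it came before or after the injection.

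The safety endpoints in SAP 4.2.3 are AEs after each vaccination, in windows of 7 days (solicited) and 30 days (unsolicited) that include the vaccination day. SAP 6.5.1 tabulates AEs over both windows, after each dose and overall.

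**The concern.** An AE that the investigator recorded as starting before the injection gets two different doses, depending on which section the programmer follows. The labels differ slightly, but these are not two variables: the sentence in 11.2.2 itself speaks of the related dose, and both entries cover AEs, medications and vaccinations. No text says which prevails, and the list of changes in SAP section 9 does not mention the matter. The SAP of 24 May 2018, reproduced in the same file, carries the same pair of rules, so the amendment did not settle it.

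Under 11.2.2, an event known to precede a dose is reported as following it. The case is a realistic one. Protocol Table 12 schedules 62 ml of blood at Visit 2, 42 ml at Visit 3 and 62 ml at Visit 7, and its study-phase labels place these draws before that day's injection. Of blood sampling, protocol 1.3.1 warns: "When taking the blood samples, the subject may feel faint; or experience mild pain, bruising". A faint during such a draw is the kind of event on which the rules disagree.

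**Working it through.** The plan states no figure on this point, so there is nothing to reproduce. The check applies each rule to an AE that starts on a scheduled vaccination day and is recorded as before the injection.

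Inputs:
- Dose days: 0, 28 and 196 in four groups; 0 and 196 in Adu1Fx (protocol Table 3).
- Allowed intervals: 28 ± 7 days and 168 ± 14 days (protocol Table 9).
- Windows: onset days 1–7 and 1–30, on the Day 1 numbering in SAP 6.5.2.
- Group size: 26 (protocol 11.4).

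Formula: onset day = event day − day of the assigned dose + 1. For 11.2.5 this assumes that onset is counted from the dose to which the event is assigned.

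| Event on | 11.2.2 | 11.2.5 | In a 30-day window under 11.2.5? |
|---|---|---|---|
| Day 0, all vaccine groups | Dose 1, day 1 | no dose | no |
| Day 28, three-dose groups | Dose 2, day 1 | Dose 1, 28 − 0 + 1 = day 29 | yes, at the planned visit |
| Day 196, three-dose groups | Dose 3, day 1 | Dose 2, 196 − 28 + 1 = day 169 | no |
| Day 196, Adu1Fx | Dose 2, day 1 | Dose 1, 196 − 0 + 1 = day 197 | no |

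Visit intervals: at Visit 3 the onset day under 11.2.5 runs from 21 + 1 = 22 to 35 + 1 = 36. The event therefore leaves Dose 1's 30-day window only when the visit falls 30 or more days after Dose 1. It is outside the 7-day window throughout. At Visit 7 in the three-dose groups the range is 154 + 1 = 155 to 182 + 1 = 183, always outside.

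Where the rules agree: for an event recorded as after the injection, or with no timing recorded, both give that day's dose and onset day 1.

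The onset-day rule: read literally, 11.2.1 gives the Day 196 event onset day 1 even after 11.2.5 has attached it to the previous dose. If the window tables select on that variable, the event is still counted. The last two rows of the table hold only if onset follows the assigned dose, so 11.2.1 has to change together with 11.2.2.

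Scale: one subject in 26 is 1/26 = 3.8 percentage points. The exact 95% interval moves from 0–13.2% (0/26) to 0.1–19.6% (1/26). This is a ceiling for a full group, because the tables count subjects with at least one AE, and a subject already counted for that dose adds nothing.

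**The case against.** The best defence of 11.2.2 is that the endpoint windows are set by calendar day and include the day of vaccination. Assigning every same-day event to that day's dose fits this, and it errs towards over-counting vaccine AEs, not hiding them. Causality is assessed separately by the investigator, so a pre-injection event judged unrelated stays out of the related-AE tables, and the safety analyses are descriptive. This stands in part: 11.2.2 alone would be a workable, cautious convention. It does not justify keeping two rules, or counting as post-vaccination an event that the investigator recorded as earlier.

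It is also fair to say that the documents do not show an eCRF field for before/after timing; 11.2.5 only says what to do if the timing was indicated.

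Three stronger readings might be inferred, and the documents support none of them.

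- *Everything before Dose 1 is medical history.* Protocol 9.1.1 does list among non-AEs "Pre-existing conditions or signs and/or symptoms present in a subject prior to the first study vaccination". The same section, however, counts as AEs those pre-treatment events that result from protocol-mandated procedures. A faint caused by the Day 0 study draw fits that entry.
- *The Day 28 event drops out of the tables under 11.2.5.* At the planned visit it stays inside Dose 1's 30-day window. Tables covering 30 days after any vaccination, counted per subject, do not change.
- *Several events will be misattributed.* Planned doses number 4 × 26 × 3 + 26 × 2 = 364. An assumed rate of 1–2% would give 3.6 to 7.3 events. No such rate is in the documents, 364 ignores the roughly 20% drop-out that protocol 11.4 expects, and the conflict reaches only events whose timing was recorded as before.

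**Conclusion.** The contradiction is real but narrow. It concerns AEs that start on a vaccination day and are recorded as before the injection. At Day 0 and Day 196 the choice of rule decides whether such an event is post-vaccination at all, provided that onset is counted from the assigned dose. At Day 28 it mainly changes the by-dose splits and the 7-day summaries. The number of such events cannot be estimated from the documents. The point touches descriptive safety tables only and leaves every efficacy result unchanged. It is a minor point, worth settling because either programming choice could claim to follow the SAP.

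**What to change.** - In SAP 11.2.2, delete the clause that applies the rule to events preceding vaccination, together with its example. Use the 11.2.5 rule throughout: recorded timing where available, otherwise that day's dose.
- In SAP 11.2.1, amend the onset-day rule so that an event recorded as before the injection is counted from the previous dose.
- State that AEs recorded as before Dose 1 are not tabulated as post-vaccination AEs. Those caused by protocol-mandated procedures remain AEs under protocol 9.1.1 and are reported separately, not moved to medical history.
- Both rules also cover medications. Say how the single rule treats prophylactic medication taken shortly before an injection, since SAP 6.5.1 summarises its use over Day 0–6.

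The cost is SAP wording and slightly more programming. The result depends on before/after timing where the investigator recorded it; elsewhere the existing default in 11.2.5 applies.
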